Of the existing prediction models in the field, the one that shows the strongest performance in the PRESCIENT sample may be made into an online risk calculator for preliminary use in some clinical settings (e.g., to allow clinical decision-making regarding the value of further assessments, such as referral for imaging), as in other areas of medicine^{e.g.121}, and to allow stratification for aetiological and treatment research. Importantly, because the PRESCIENT dataset will include participants recruited from both primary and specialist service settings (*headspace* and HEPs/Orygen), the risk calculator will be able to be calibrated for type of recruitment/service setting, which has been found to be an important factor in risk prediction in this field¹²². This use of the PRESCIENT dataset to externally validate existing and forthcoming prediction models will address one of the key limitations in the field⁹, namely the lack of robust validation procedures on prediction models.

Developing new prediction models (specific aim 2c)

Critically, the PRESCIENT dataset will facilitate the development of new, more refined prediction models, and associated risk calculators, that take advances in the field into account (such as iterative and dynamic prediction, see 2.3) and which directly address the limitations identified in the field (lack of internal and external validation; low ratio of converted cases to number of predictor variables; lack of pre-selection of predictor variables; inappropriate methods of presenting model performance; not covarying for treatment received; insufficient use of clinical

comparison groups^{9, 123, 124}). Data from the PRESCIENT and ProNET networks will be combined (i.e., the AMP SCZ dataset) for the development of these new prediction models. The primary purpose of these new prediction models will be to guide stratification of patients in future pharmacological clinical trials, in line with the overarching aim of AMP SCZ to develop new treatments for the CHR stage of illness.

There are a number of reasons that the AMP SCZ dataset will be able to *improve* on prediction models based on existing datasets and which may be far more useful for treatment decision-making and treatment development:

1. *Scale and multimodal data*: The size of the dataset (approximate CHR n of 2000) and the comprehensive suite of multimodal data will provide greater predictive accuracy in model development and allow the integration of multiple data types.

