
2. *Dynamic prediction*: There is compelling preliminary evidence that using repeat assessments over time can enhance predictive performance and provide early warning signs of deterioration or lack of treatment response. This modelling requires time series data, which is not extensively available in existing data sets, but will be collected in this new network. A variety of methods will be used to collect the required data (see 8.1 Schedule of Assessments): repeat biomarker data to examine predictive value of biomarker trajectories; in-person and online clinical, neurocognitive, and speech data; and digital assessment methods, including EMA and passive sensing (actigraphy and geolocation). The research team has developed and has access to world leading applications for both EMA and passive sensing. These dynamic aspects of predictive modelling may provide risk calculations based on trajectories in individual-level data and which can be updated over time in response to incoming information, providing recommendations for change in treatment approach (e.g., increase in risk indicating the need for intensification of treatment). They also have the potential to provide 'real time' indications of imminent deterioration in mental state.

3. *Modelling impact of treatment*: Most CHR patients included in research cohorts receive psychosocial and/or pharmacological treatment, even if 'standard care' rather than controlled trial treatment. There has been increased recognition in recent years that this treatment (both as pre-emptive and for presenting complaints) *influences outcomes*, i.e., prediction models may in fact be modelling treatment response rather than natural course of disorder, or possibly an interaction between the two^{123, 125}. The impact of type/degree of treatment components delivered (e.g., psychosocial interventions, medications, nutritional supplements, etc.) will be captured and incorporated into predictive modelling.

Both traditional statistical and machine learning approaches will be deployed in development of prediction models. Statistical approaches will include Cox regression and joint modelling. While the selection of variables to be measured in the study are already informed by their predictive performance in previous studies, variable selection methods including LASSO and stepwise selection will be used to select

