potential predictors in the final model. The candidate predictors include the range of multimodal assessments outlined in 8.1. Due to the high number of predictor variables, data reduction procedures may be used. Internal validation of the model will be conducted using bootstrap validation (a resampling technique). The performance of the prediction models will be assessed using measures such as sensitivity, specificity and concordance index (which should be at least 0.7 for good predictive performance). Machine learning approaches will include support vector machine (SVM) algorithms using model training and leave-one-site-out cross validation.

External validation (specific aim 3)

If a strong prediction model can be obtained, further evaluation of the prediction model will be conducted by using an external validation sub-sample from the AMP SCZ cohort. Data from a subset of sites across the two networks will be held back from the initial model development phase in order to externally validate the performance of the model. This will test the replicability of the model's performance and the generalisability of the findings to diverse healthcare settings. Calibration performance of the model will be assessed using calibration plot (plot of predicted outcome probabilities against observed outcome frequencies) and tests for calibration intercept and slope. Discrimination performance will be assessed using measures such as sensitivity, specificity and concordance index.

15. Publication and Use of Study Findings

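### Unpenalised stepwise selection is named on a par with LASSO for a large, unbounded candidate pool and about 300 conversions or fewer, which risks predicted risks that are too extreme

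*Protocol*

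**What the plan says.** Section 14, on new prediction models (aim 2c), lists limitations of earlier work that the new models are to address directly. Two matter here: "low ratio of converted cases to number of predictor variables" and "lack of pre-selection of predictor variables".

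It then states how predictors reach the final model. It first says that "the selection of variables to be measured in the study are already informed by their predictive performance in previous studies", and continues that "variable selection methods including LASSO and stepwise selection will be used to select" them. Neither method has priority, and no entry or stay rule is given for stepwise selection. On the pool: "The candidate predictors include the range of multimodal assessments outlined in 8.1". On its size: "Due to the high number of predictor variables, data reduction procedures may be used".

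On checking: "Internal validation of the model will be conducted using bootstrap validation (a resampling technique"). The development-stage performance measures given as examples are sensitivity, specificity and the concordance index, with 0.7 as the mark of good performance. A calibration plot and tests of calibration intercept and slope appear under external validation (aim 3), which takes place only if a strong model is obtained. For that step, "Data from a subset of sites across the two networks will be held back from the initial model development phase"; the size of the subset is not given.

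Section 7.2 expects 1,977 CHR participants and 300 conversions, and calls more than 30 parameters undesirable because the model would be unwieldy in practice.

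**The concern.** Stepwise selection keeps a predictor because its estimate happened to come out large in the development data, and then applies no shrinkage. The more candidates it searches per event, the more the retained coefficients overstate the truth. The resulting model spreads predicted risks too widely: high risks too high, low risks too low.

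Nothing in the text limits the search. Choosing which instruments to administer does not cap the number of variables derived from them. Data reduction is optional. The 30-parameter limit concerns the usability of the finished model, not the number of candidates tried on the way to it.

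Calibration matters because the intended output is an individual probability of conversion. Section 15.3 foresees it informing decisions about monitoring and treatment, and Section 14 foresees it guiding stratification in later drug trials.

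**Working it through.** **1. The plan's own figures.** Section 7.2: 937 + 1,040 = 1,977, and 0.15 × 1,977 = 296.6 conversions against the stated 300, which agree. Table 1 for 30 parameters gives 1,265 / 1,193 / 1,098 (low / medium / high performance). These follow from the shrinkage criterion n = p / [(S − 1) ln(1 − R²/S)] with S = 0.9 and R² back-solved from the table as about 0.190, 0.200 and 0.215. For example, 30 / [−0.1 × ln(1 − 0.190/0.9)] = 30 / 0.02371 = 1,265. All 15 cells return to within 2 participants. This confirms the formula, not the R² inputs, which the protocol does not state.

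**2. Conversions per candidate.** Events divided by candidates. The candidate counts and the one-third hold-out are assumptions; 0.15 × 1,318 = 197.7.

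| Candidates | All 1,977 (296.6 events) | One third held back (197.7 events) |
|---|---|---|
| 30 | 9.9 | 6.6 |
| 50 | 5.9 | 4.0 |
| 100 | 3.0 | 2.0 |
| 200 | 1.5 | 1.0 |

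**3. Calibration in new participants.** Cox simulation with 15% events by 24 months and development n of 1,977 or 1,318. Forward-backward stepwise selection (p < 0.05, AIC or BIC; AIC only up to 100 candidates) was compared with LASSO using a 5-fold cross-validated penalty, all tested in 8,000 new subjects. Assumptions not in the protocol: candidates in blocks of 10 correlated at 0.3; signal sparse (8 true predictors), moderate (20) or diffuse (all); true concordance about 0.75 (30 runs per setting) or 0.69 (15 runs). The slope is the coefficient of the model's linear predictor when refitted in new data; 1 means no overfitting.

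Stepwise at p < 0.05, n = 1,977, true concordance 0.75, range over signal types:

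| Candidates | Calibration slope |
|---|---|
| 30 | 0.89–0.95 |
| 50 | 0.82–0.93 |
| 100 | 0.71–0.89 |
| 200 | 0.53–0.77 |

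At true concordance 0.69 and 100 candidates, the p < 0.05 slopes were 0.84 (sparse), 0.76 (moderate) and 0.63 (diffuse) at n = 1,977, and 0.70, 0.64 and 0.53 at n = 1,318. Over all settings and entry rules, stepwise slopes ran from 0.32 to 0.96, always below 1. LASSO slopes ran from 0.88 to 1.43, often above 1, meaning over-shrunk.

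To read a slope: at 0.75, someone predicted at 4 times the average hazard is truly at about 4^0.75 = 2.8 times.

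**4. Discrimination.** Stepwise minus LASSO concordance in new data was usually 0.00 to −0.02; the worst was −0.037 (BIC, diffuse, 200 candidates). Under a sparse signal with true concordance 0.75, stepwise was sometimes slightly better: +0.001 to +0.003 (p < 0.05, 30–50 candidates) and +0.003 to +0.006 (BIC, 50–100 candidates). The fall from apparent to new-data concordance does not separate the methods. With 100 diffuse candidates at n = 1,977, stepwise fell from 0.754 to 0.696 (0.058) and LASSO from 0.772 to 0.710 (0.062).

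**5. What the bootstrap would show.** The bootstrap-corrected slope is the mean slope of models fitted in resamples and evaluated in the original data. Two logistic simulations (about 14–15% events, 20 true predictors, 50–100 candidates, n = 1,318 to 1,977) compared refitting only the selected model with repeating the selection in each resample.

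| Run | Slope in new data | Selected model only | Selection repeated |
|---|---|---|---|
| First | 0.74–0.78 | 0.93–0.95 | 0.72–0.84 |
| Second (backward p < 0.05; 12 replicates, 12 resamples each) | 0.63–0.80 | 0.89–0.92 | 0.61–0.80 |

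In the second run the AUC in new data was 0.681–0.708. The selected-model bootstrap reported 0.727–0.742, clear of the protocol's 0.7 mark; repeating the selection reported 0.677–0.705.

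**The case against.** Section 14 calls itself an outline whose details are to be settled with the coordinating centre, and a statistical analysis plan may exist that is not shown. LASSO is already named, and named first. Earlier evidence did guide the choice of measures: Section 5.3.4 gives the rationale domain by domain and tabulates which EEG measures predict conversion. Data reduction is allowed. Calibration slope and intercept are to be tested in held-back sites, which is a check that would expose an overfitted model, and the development-stage measures are only examples. With about 30 candidates the miscalibration is mild.

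Much of this stands, and it keeps the point moderate. It does not remove it. The protocol states that stepwise selection will be used to build the final model, so this is a named method, not a detail left open. The evidence-based choice of measures leaves the number of candidates unbounded, and data reduction is only a possibility. The external calibration check comes after development and only for a model already judged strong, a judgement that internal validation may inform.

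**Conclusion.** The point holds as a moderate one. With about 297 conversions or fewer and a candidate pool of unstated size, unpenalised stepwise selection risks overfitted, poorly calibrated predictions. Slopes are about 0.9 with 30 candidates, about 0.7 to 0.9 with 100, and lower with more candidates, a diffuse signal or a smaller development set. The direction was the same in every setting tried. The size rests on assumed candidate counts, correlation, signal structure and hold-out, none of which the protocol gives, and on 15 to 30 runs per setting.

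Three stronger readings are tempting but not supported:

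- A reader might infer that Section 14 flatly contradicts itself on pre-selection. It does not: the sentence that names stepwise selection opens by claiming evidence-based choice of the measured variables. What remains is that this choice does not bound the candidates.
- A reader might infer that stepwise selection is less accurate than LASSO at this sample size. The loss in concordance is usually 0.00 to 0.02 and reverses in some sparse-signal settings. The consistent defect is calibration.
- A reader might infer that only the finally selected model will be bootstrapped. The text is silent on this; the figures in step 5 show what would follow if it were done that way.

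**What to change.** In Section 14:

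- Remove stepwise selection, or keep it only as a labelled sensitivity analysis.
- Make penalised Cox regression (LASSO or elastic net, penalty chosen by cross-validation) the selection method.
- Fix the candidate list before outcome data are examined.
- State that every data-driven step (data reduction, selection and tuning) is repeated within each bootstrap resample.
- Report the optimism-corrected calibration slope beside the concordance index at the development stage, whether or not the model goes on to external validation.

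The cost is wording and computing time. Two downsides should be accepted openly. A penalised model may retain more predictors: in a separate logistic simulation with 45 candidates, LASSO kept about 18 against 7 to 13 for stepwise. LASSO can also over-shrink, which the reported slope would reveal.

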15.1 Publications

The research team will follow the publication guidelines set out in Section 4 (Publication and dissemination of research findings) and Section 5 (Authorship) of the 2007 Australian Code for the Conduct of Research. An AMP SCZ publication policy has been established with the funding body, NIMH, outlining the types of research papers that will be published using this dataset and authorship designations. All research findings, whether containing negative or positive results, will be disseminated accurately. After approval by the coordinating/Principal Investigator, co-investigators and biostatisticians, results of the study will be published in peer-reviewed scientific journals and presented at scientific conferences. The final results will be published after termination of the study. Where participants have asked to see the results of the study, these results will be provided to them in due course. AMP

SCZ data and analyses will be made publicly available to suitably qualified researchers through the NIMH Data Archive.

15.2 NIMH Data Archive

The <https://nda.nih.gov/> will provide cloud-based infrastructure to facilitate storage and analysis of AMP SCZ data. The data archive currently holds raw and derived data collected from a total of 500,000 research participants using a variety of measures, including clinical, imaging, electrophysiological, cognitive, genetic, and outcome data. All AMP SCZ data stored in the archive will adhere to the NIMH Data Archive (NDA) terms and conditions and the NIMH Data Sharing Policy. Specifically, participant data will be transferred in a privacy-enabled manner and will be protected by practices that include the removal of any personally identifiable information; accredited users will be given secure, role-based access to the data. The archive includes data dictionaries to describe and enable efficient searches across the diverse types of data.

The NDA will make curated AMP SCZ data available to the broader research community on a 6-monthly basis, in accordance with 'open science' principles. The NDA will also work with the DPACC to make data analysis pipelines available to the research community. The NDA requires safeguards and institutional protections and monitoring with clear guidelines for data use. Only investigators at approved institutions are permitted to submit a data use certification to the NDA. This is a legal document that an institution signs on behalf of the investigator. Investigators approved to access the data and their institutions must pledge not to attempt to identify any participant. Data use is restricted to research purposes only. Additionally, geolocation data is treated in the NDA with the additional safeguard that approved investigators and institutions must also receive local ethics committee approval from their institution to access the data and must undergo ongoing local ethics committee oversight.

The NDA, established in 2006, is sustained on an ongoing basis through NIMH funds.

15.3 Clinical Tool Development

As noted above, the prediction models developed through this program of work may lead to the development of clinical prediction tools. Although the precise nature of these clinical prediction tools are yet to be decided, an outline of the likely process is provided below.

The expectation is that, if a prediction model with strong performance can be obtained, the model will be accessible to clinicians and other interested parties either online, via a code repository, or through publications. Specifically, by inputting the values of the predictors from a particular individual into the model, the intent is for the prediction model to estimate the probability of conversion to psychosis (primary outcome of interest) for that individual. This probability can be regarded as a risk score and can aid clinicians to make decisions about appropriate level of monitoring, type, and duration of treatment. Examples of such prototype clinical tools (“risk calculators”) are available at these online links: <https://apps.konsta.com.pl/app/transpsych/#>, <http://riskcalc.org:3838/napls/>¹²⁶. Due to the repeat assessments and digital momentary assessments conducted in the current study, a clinical tool that provides dynamic prediction may also be developed. This would involve inputting data collected over time for a particular patient, with the “risk calculator” being updated with this newly inputted information. Further evaluation of this clinical tool will be conducted by using decision analysis to assess the clinical value of the tool by taking into account the decisions that clinicians and patients would need to make with regard to possible interventions¹²⁷. This future work will further test and refine the clinical tool.

16. Funding

This study is funded by the National Institute of Mental Health (NIMH), US.

17. Outcomes and Significance

Psychotic illnesses usually first emerge in young people and result in widespread suffering, protracted disability, premature death, and a huge economic burden. Early intervention represents a vital strategy to reduce this burden. Psychotic disorders are preceded by a prodromal period of distress, impaired functioning and subthreshold symptomatology. Our original research operationally defined the Clinical High Risk state, which predicts a substantially increased risk of incipient psychosis. There is substantial heterogeneity in clinical trajectories in the CHR population. The field is currently unable to reliably identify these trajectories early on, particularly on an individual patient level. The models to date (using clinical, neurocognitive, neuroimaging, neurobiological and genetic data) have yielded only modest predictive value for conversion to psychotic disorder and other outcomes. This presents a

challenge for targeted intervention development and developing robust aetiological models.

The current large consortia-based project seeks to develop more robust prediction models for a range of outcomes in the CHR population (conversion to psychotic disorder, persistent and incident non-psychotic disorder, non-remission of CHR status, persistent negative symptoms, full recovery, functional outcome) and advance the introduction of risk prediction tools in clinical practice. These prediction models and associated clinical tools will be developed using multimodal data consisting of biomarkers (neuroimaging, neurocognition, neurophysiology, biospecimens), clinical data, and digital momentary assessments. The prediction models will facilitate selection of CHR patients for enrolment in clinical trials (patient stratification) and point towards targets for aetiological research and novel treatments. They will also serve as measures of early treatment effects and provide tools for monitoring disease progression and clinical and functional outcomes.

18. References

Appendix A

Antipsychotic Dose Equivalents

The doses provided in the table below are currently equivalent to a haloperidol dose of 50 mg. The RA must seek out the latest dose equivalent at the time of entry into the study for each participant this relates to.

Abbreviated Drug Name, Drug Name and Trade name		Dose in mg
AMS	Amisulpiride (Solian)	1875
APP	Aripiprazole (Abilitat, Abilify)	187.5
ASP	Asenapine (Saphris)	125
BRX	Brexpiprazole (Rexulti)	25
CRP	Cariprazine (Vraylar)	18.75
CPZ	Chlorpromazine (Largactil)	2500
CLZ	Clozapine (Clozaril)	2500
DPL	Droperidol (Droleptan)	100
FLH	Fluphenazine HCL (Anatensol)	50
HPL	Haloperidol (Haldol)	50
ILO	Iloperidone (Fanapt)	100
LUM	Lumateperone (Caplyta)	525
LUR	Lurasidone (Latuda)	1500
OLZ	Olanzapine (Zyprexa)	125
PAL	Paliperidone (Invega)	50
PCZ	Pericyazine (Neulactil)	250
PIM	Pimozide (Orap)	50
PPH	Perphenazine (Trilafon)	200
QTP	Quetiapine Fumarate (Seroquel)	1875
RIS/RSP	Risperidone (Risperdal)	50
SUL	Sulpiride (Dolmatil, Sulpitil, Sulparex)	5000
THI	Thiothixene (Navane)	100
THZ	Thioridazine (Melleril, Aldazine)	2500
TPZ	Trifluoperazine (Stelazine)	125
ZPD	Ziprasidone (Geodon)	1500
